7.8.7. Exploratory objective: X-ray Dose**Objective**

- To assess the total X-ray dose (DAP, AK) related to PCI in the Dynamic Coronary Roadmap and control group

Endpoint

- The average total DAP and AK per PCI (from first positioning the interventional guiding catheter in stable coronary position till end of PCI procedure) measured by the Philips X-ray system.

Analysis

The objective will be evaluated using a two-sample equal-variance t-test.

All subjects will be included in this analysis.

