8.4 Demographics and Baseline Characteristics

Demographic and baseline variables will be summarized by treatment group for subjects in the Full Analysis Population (FAP). Age (years), height (cm), weight (kg) and body mass index (BMI) (kg/m^2) will be summarized as continuous data. Gender (Male/Female) and race (African American (Black), Non-African American, Unknown) will be summarized as categorical data.

We will perform statistical tests to compare the baseline characteristics of the two groups to check that the control and Dynamic Coronary Roadmap groups are similar at the start of the study. For categorical variables, we will perform a Chi-2 or Fisher Exact test, and for continuous variables a t-test or Wilcoxon-Mann-Whitney test as appropriate. When the groups are not comparable regarding baseline characteristics, adjustment for covariates will be applied as a sensitivity analysis (see section 8.14).

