8.11.3.7 X-ray Dose

The total DAP and AK per PCI (from first positioning the interventional guiding catheter in stable coronary position till end of PCI procedure) by treatment group.

Descriptive summaries of the total DAP (Gy*cm²) and AK (mGy) per PCI will be presented by treatment group for the FAP and will include the number of subjects with non-missing data (n), mean with 95% confidence interval, standard deviation (SD), median, interquartile range (IQR) and minimum and maximum values.

The total DAP and AK will be evaluated separately using one-sided two-sample t-tests. We will test for assumptions, e.g. normality and equal variances. Normality will be checked using histograms and Q-Q plots. If there are strong indications of non-normality, the data will be (log)transformed, and the back transformed results will be presented. Levene's test for equality of variances will be applied. When the p-value of this test is greater than 0.05, then we assume the variances are equal and we will use the arithmetic mean of the variances in

Document ID:	<As applicable, per local requirements>	Document title:		Classification:	For internal use
		Statistical Analysis Plan			
Modified:	11MAY2023			Author:	
Version:	3.0	Template ID:	ClinicalStudyTemplate0025	Approver:	
Status:	Final	Template Version Date:	02MAR2018	Page:	35 of 52

Statistical Analysis Plan

calculating the standard error. When the p-value is less than or equal to 0.05, then we assume the variances are unequal and then we will calculate the standard error from the weighted average of the two variances.

The results of the t-test will be displayed as estimates of the between treatment group difference (with 95% confidence intervals) and the (one-sided) p-value for the between treatment group difference. When the p-value is lower than the significance level of 2.5% (alpha) we will reject the null hypothesis.

All subjects in the FAP population will be included in this analysis. The analysis will be repeated for the PP population.

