8.14 Adjustment for Covariates

Analyses to determine whether there is an effect based on e.g. intervention difficulty (as measured by the SYNTAX score), lesion characteristics, patient demographics, physician experience, center etc. will be performed. If an effect on the primary or secondary endpoint is found, applying adjustment analysis will be considered. As a sensitivity analysis, we will then perform an analysis

Document ID:	<As applicable, per local requirements>	Document title:		Classification:	For internal use
Modified:	11MAY2023	Statistical Analysis Plan		Author:	
Version:	3.0	Template ID:	ClinicalStudyTemplate0025	Approver:	
Status:	Final	Template Version Date:	02MAR2018	Page:	38 of 52

Statistical Analysis Plan

of covariance (ANCOVA) for the primary and/or the secondary endpoint adjusting for covariates which are deemed important. The results of the ANCOVA will be displayed through Least-Squares Means (LSMEANS) estimates of the between treatment group difference (with 95% confidence intervals) and the p-value for the between treatment group difference adjusted for covariates.

To investigate whether there is a center effect on the primary outcome, we will calculate the Intra Class Correlation coefficient (ICC) of the total iodinated contrast volume between centers. The ICC is the ratio of the variability between centers to the total variance. The ICC measures to what extent the proportion of the total variability of the primary outcome is accounted for by the clustering of patients within centers. If the ICC is higher than 0.10 we will perform a random effects model on the primary outcome with center as a random effect and treatment as a fixed effect. We will also check the distribution of baseline characteristics between centers. If the centers differ in characteristics, which may influence the primary outcome, such as intervention difficulty, lesion characteristics, patient demographics, physician experience etc, we will perform a random effects model on the primary outcome with center as a random effect and treatment and other covariates as fixed effects (ANCOVA) as a sensitivity analysis. The results of the ANCOVA will be displayed through Least-Squares Means (LSMEANS) estimates of the between treatment group difference (with 95% confidence intervals) and the p-value for the between treatment group difference adjusted for covariates.

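### X-ray dose (DAP and AK) is compared without adjusting for BMI, and no specified analysis covers this; pre-specifying a BMI-adjusted model would be a nearly free gain in precision for an exploratory endpoint

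*SAP*

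**What the plan says.** Dose is an exploratory objective in both documents. Protocol 7.8.7 plans no covariate: "The objective will be evaluated using a two-sample equal-variance t-test". SAP 8.11.3.7 keeps the unadjusted form: "The total DAP and AK will be evaluated separately using one-sided two-sample t-tests". It allows a log transformation if the data are clearly non-normal, reports a between-group difference with a 95% CI, and sets a formal decision rule: "When the p-value is lower than the significance level of 2.5% (alpha) we will reject the null hypothesis".

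BMI is among the variables that SAP 8.4 summarises as continuous in the Full Analysis Population. Randomisation is stratified by site, type of PCI and number of vessels (SAP 4.4.2), so BMI is balanced only by chance.

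Three places speak of adjustment:

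- SAP 8.4, after tests comparing the arms at baseline: "When the groups are not comparable regarding baseline characteristics, adjustment for covariates will be applied as a sensitivity analysis (see section 8.14").
- SAP 8.14, which sets the trigger ("If an effect on the primary or secondary endpoint is found, applying adjustment analysis will be considered") and then specifies an analysis "of covariance (ANCOVA) for the primary and/or the secondary endpoint adjusting for covariates which are deemed important". Its centre-effect models concern the primary outcome only.
- Protocol 7.2 and SAP 4.5, which list patient demographics among factors to examine and say that adjustment will be considered. Neither names dose or BMI.

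**The concern.** If BMI correlates with dose, an unadjusted comparison leaves BMI-related spread in the error term, so the confidence interval for the device effect on DAP and AK is wider than it need be. A chance difference in BMI between arms would also pass into the estimated dose difference, where it could imitate or mask a device effect. The dose results will carry p-values and a reject-or-not rule at one-sided 2.5%. A reader may therefore take them as evidence on whether a fluoroscopic overlay changes radiation exposure. The adjustment is credible only if written down in advance: adding BMI after the dose results are known would look like a choice made for its effect.

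**Working it through.** **1. The plan's own figures.** The documents give no SD, effect size or power for DAP or AK. The nearest figure is the primary-endpoint sample size (SAP 8.1.1): means 152.1 and 129.3 ml, SD 73.0, one-sided α = 0.025. The standardised effect is 22.8/73.0 = 0.3123. The noncentral t gives power 79.8% at 161 per group and 80.03% at 162, so 162 reproduces, and 162/0.9 = 180. This concerns contrast volume, not dose. For dose I use 177 evaluable per group, the figure in SAP 8.1.2 before inflation for 10% drop-out (177/0.9 = 196.7, rounded up to 197).

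**2. Assumption.** R² is the share of within-arm variance in dose, on the analysis scale, explained by BMI. The documents give no value, so I take 0.01 to 0.4.

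**3. Precision.** ANCOVA multiplies the residual SD by √(1 − R²). The CI narrows by 1 − √(1 − R²), and the gain equals multiplying the sample size by 1/(1 − R²).

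**4. Power.** As a neutral benchmark, take the effect that the plain t-test detects with 80% power at 177 per group, 0.299 SD. Power with BMI in the model comes from the noncentral t with 351 degrees of freedom and noncentrality (0.299/√(1 − R²)) × √(177/2).

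**5. Chance imbalance.** The standardised BMI difference between arms has SE √(2/177) = 0.106. An imbalance of 1.5 SE is 1.5 × 0.106 = 0.16 SD of BMI, or 0.8 kg/m² if the BMI SD is 5 (assumed). The chance of an imbalance at least that large in one given direction is 1 − Φ(1.5) = 6.7%. Given an imbalance of exactly 1.5 SE, the unadjusted statistic has mean 1.5√R² and variance 1 − R² under the null. The conditional one-sided error in the favoured direction is therefore 1 − Φ((1.96 − 1.5√R²)/√(1 − R²)). For R² = 0.1 this is 1 − Φ((1.96 − 0.474)/0.949) = 1 − Φ(1.566) = 5.9%.

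| R² | CI narrower by | Equivalent sample size | Power (80% unadjusted) | Conditional error at 1.5 SE |
|---|---|---|---|---|
| 0.01 | 0.5% | ×1.01 | 80.4% | 3.4% |
| 0.04 | 2.0% | ×1.04 | 81.6% | 4.5% |
| 0.1 | 5.1% | ×1.11 | 84.0% | 5.9% |
| 0.2 | 10.6% | ×1.25 | 88.0% | 7.5% |
| 0.3 | 16.3% | ×1.43 | 91.8% | 8.7% |
| 0.4 | 22.5% | ×1.67 | 95.1% | 9.6% |

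Averaged over all possible BMI imbalances, the unadjusted error is 2.5% at every R²: the excess in one direction is offset in the other.

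**6. Would the SAP 8.4 route catch it?** A 1.5 SE imbalance has a two-sided p-value of 0.13, so a baseline test at the usual 5% level would not flag it (8.4 states no level). Nor does a trigger based on imbalance recover precision when the arms happen to be balanced. When it does fire, it leads to 8.14, whose ANCOVA does not name dose.

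**The case against.** The strongest reply is that nothing here is an error. In a 1:1 randomised trial the unadjusted t-test is valid, and leaving an exploratory endpoint unadjusted is common and defensible. Dose is one of nine exploratory objectives, has no power target, and bears on neither the primary nor the secondary conclusion. All of that stands.

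The second reply is that imbalance is already dealt with. The SAP 8.4 sentence names no endpoint, and Protocol 7.2 and SAP 4.5 speak of adjustment generally. This stands in part: it would be wrong to say that the plan ignores baseline imbalance. But 8.4 hands over to 8.14, which is confined to the primary and/or secondary endpoint, and the other two passages commit only to considering adjustment. Whether the 8.4 promise reaches dose is unclear.

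The third reply is that the premise comes from outside the documents. A reader might infer that BMI is a main determinant of dose and is on file for every subject. Neither document says so: they give no BMI-dose correlation, and a plan to summarise BMI does not show that it is complete. With weak correlation (R² of 0.01 to 0.04) the gain is only 0.5% to 2%. This limits the size of the point but not its direction: with over 350 subjects, one uninformative covariate costs almost nothing.

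**Conclusion.** The point holds as a low-cost improvement to an exploratory analysis. Dose is compared without adjustment, BMI is a planned baseline variable, and no specified analysis adjusts dose for it. The benefit depends on an R² that the documents do not supply: across 0.01 to 0.4 the CI narrows by 0.5% to 23%, and the conditional one-sided error at a 1.5 SE imbalance is about 3% to 10%, against a nominal 2.5%. Imbalances at least that large in the unfavourable direction occur in about 7% of randomisations.

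A reader might go further and infer that the dose test has an inflated false-positive rate, or that the trial's main conclusion is at risk. Neither follows: average type I error is 2.5%, and contrast volume and angiogram counts are unaffected.

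**What to change.** In SAP 8.11.3.7, pre-specify an ANCOVA of DAP and of AK, each on the scale the SAP settles on for it, with treatment and continuous baseline BMI as terms, preferably with the randomisation stratification factors (site, type of PCI, number of vessels). Report the adjusted difference, or the ratio if log-transformed, with its 95% CI. State a simple rule for missing height or weight, such as imputing the overall mean BMI without regard to arm. Keep the unadjusted comparison as supportive or descriptive. Add a line in 8.4 or 8.14 saying which endpoints the imbalance-triggered adjustment covers.

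The cost is SAP wording and one model per dose measure. It needs no new data, procedures or subjects, but it should be fixed before the dose results are seen.

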8.11.3.8 Procedural Success

The total number and percentage of subjects treated with procedural success by treatment group. Procedural success is defined as an open target vessel with a maximum of 30% residual stenosis and TIMI flow grade 3 (complete perfusion) [TIMI 1985], e.g. determined via visual inspection of Coronary Angiography.

Descriptive summaries of procedural success will be presented by treatment group for the FAP and the PP population and will include the number of subjects with non-missing data (n), percentages and 95% exact confidence intervals.

The between treatment group difference in procedural success will be tested using a Chi-square test. If a Chi square analysis is not possible (i.e. >20% of the expected cell frequencies less than 5), then a Fisher's exact test will be performed instead. The two-sided p-value of this test will be presented. When the p-value is lower than the significance level of 5% (alpha) we will reject the null hypothesis of equal procedural success in both treatment groups.

All subjects in the FAP population will be included in this analysis. The analysis will be repeated for the PP population.

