7.8.8. Exploratory objective: Procedural Success**Objective**

- To assess the procedural success in the Dynamic Coronary Roadmap and control group

Endpoint

- The total number and percentage of subjects treated with procedural success. Procedural success is defined as an open target vessel with a maximum of 30% residual stenosis and TIMI flow grade 3 (complete perfusion) [TIMI 1985], e.g. determined via visual inspection of Coronary Angiography.

Analysis

Since DCR is a tool assisting the physician in navigating devices through the coronary arteries it is not likely this trial will find a significant difference in procedural success in the DCR group compared to the control group.

The objective will be evaluated using a two-sample equal-variance t-test.

All subjects will be included in this analysis.

IGT Systems	Post-Market Clinical Study Protocol DCR4Contrast Clinical Evidence Study	Doc ID: XCY612-130576 Rev: 02 Page 26 of 33
-------------	-----------------------------------------------------------------------------	---------------------------------------------------

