8.2.1 Analysis Population

The following analysis populations will be defined in this study.

Enrolled Population

The enrolled population is defined as all subjects who signed informed consent.

Randomized population

The randomised population is defined as all randomised subjects, defined as any subject with a randomisation result as recorded in the eCRF.

Analysis of data using the randomised population will consider allocation of subjects to treatment groups as randomised.

Full Analysis Population

The full analysis population (FAP) is defined as all randomised subjects who underwent a PCI in at least one vessel without the use of OCT and/or rotational or orbital atherectomy of which the primary endpoint and/or the secondary endpoint is available.

Analysis of data using the Full analysis population will consider allocation of subjects to treatment groups as randomised.

Safety population

The safety analysis population (SAF) is defined as all randomised subjects who underwent a(n) attempt to PCI or another procedure (for example CABG).

Analysis of data using the Safety population will consider allocation of subjects to treatment groups as treated (i.e. will be based on the actual treatment a subject has received regardless of which treatment they were randomised to receive).

In case the safety population is equal to the full analysis population, only the results of the full analysis population will be presented.

Per Protocol population

The Per Protocol population is defined as all FAP subjects without major protocol violations. Protocol violations are failures to adhere to the inclusion/exclusion criteria and protocol requirements and will be divided into major protocol violations and minor protocol violations. Major protocol violations are those that are considered to have a significant effect on the treatment efficacy and hence would exclude the subject from the PP population. Minor protocol violations are those that are not considered to significantly affect the efficacy evaluation and

Document ID:	<As applicable, per local requirements>	Document title:	Classification:	For internal use
Modified:	11MAY2023	Statistical Analysis Plan		
Version:	3.0	Template ID:	ClinicalStudyTemplate0025	Approver:
Status:	Final	Template Version Date:	02MAR2018	Page: 24 of 52

Statistical Analysis Plan

hence do not warrant subjects' exclusion from the PP population. Major protocol violations will be identified by a Data Review Meeting prior to database lock.

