8.11.3.9 In-hospital MACCE

The total number and percentage of in-hospital MACCE. MACCE is defined as one or more of the following events: All cause death, Acute Myocardial Infarction (AMI), Coronary Artery Bypass Grafting (CABG), Repeat Coronary Revascularization of the target lesion, Acute Ischemic Stroke (AIS) during hospitalization for the PCI procedure.

Document ID:	<As applicable, per local requirements>	Document title:		Classification:	For internal use
		Statistical Analysis Plan			
Modified:	11MAY2023			Author:	
Version:	3.0	Template ID:	ClinicalStudyTemplate0025	Approver:	
Status:	Final	Template Version Date:	02MAR2018	Page:	36 of 52

Statistical Analysis Plan

Descriptive summaries of MACCE will be presented by treatment group for the FAP and the PP population and will include the number of subjects with non-missing data (n), percentages and 95% exact confidence intervals.

The between treatment group difference in MACCE will be tested using a Chi-square test. If a Chi square analysis is not possible (i.e. >20% of the expected cell frequencies less than 5), then a Fisher's exact test will be performed instead. The two-sided p-value of this test will be presented. When the p-value is lower than the significance level of 5% (alpha) we will reject the null hypothesis of equal in-hospital MACCE in both treatment groups.

All subjects in the FAP population will be included in this analysis. The analysis will be repeated for the PP population.

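### Procedural success and in-hospital MACCE are tested only in subjects who underwent a PCI in at least one vessel, so attempt-only and CABG-instead cases never enter an as-randomised comparison

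*SAP*

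**What the plan says.** SAP 8.2.1 defines the FAP as "all randomised subjects who underwent a PCI in at least one vessel without the use of OCT and/or rotational or orbital atherectomy", with a primary and/or secondary endpoint value available. It is analysed as randomised. The PP population is the part of the FAP without major violations. The Safety population (SAF) is wider: it takes in randomised subjects with an "attempt to PCI or another procedure (for example CABG", and it is analysed by treatment actually received.

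SAP 8.11.3.8 says "The between treatment group difference in procedural success will be tested using a Chi-square test", with Fisher's exact test when more than 20% of expected cell counts are below 5, at two-sided 5%. SAP 8.11.3.9 says "The between treatment group difference in MACCE will be tested using a Chi-square test" under the same rule, and on a small p-value "we will reject the null hypothesis of equal in-hospital MACCE in both treatment groups". On the population, SAP 8.11.3.8 states "All subjects in the FAP population will be included in this analysis. The analysis will be repeated for the PP population", and SAP 8.11.3.9 uses the same two sets.

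Protocol 7.8.8 defines the success endpoint as "The total number and percentage of subjects treated with procedural success", and 7.8.8 and 7.8.9 both include all subjects. For MACCE the protocol plans frequencies and percentages only. SAP 9.2 declares the move from all subjects to FAP and PP, but does not list the added MACCE test.

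**The concern.** Success means an open target vessel with at most 30% residual stenosis and TIMI grade 3 flow. A procedure in which no vessel was treated cannot meet that. CABG during the hospitalisation is a MACCE component. Entry to the tested set therefore depends on something that happens after randomisation and that can itself be the outcome. The trial is unblinded, so a decision to abandon or convert can depend on the arm.

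At stake is whether the plan can show that using the roadmap does not change how often procedures fail or convert. If one arm had more abandoned or converted cases, neither test would contain them. If the arms had equal numbers, the difference would be sound, but the success rate would look better than it was.

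**Working it through.** **1. Who is in which set (SAP 8.2.1).**

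| Randomised subject, no OCT or atherectomy, endpoint value available where PCI was done | FAP | SAF | Counts as |
|---|---|---|---|
| PCI done, residual stenosis above 30% or TIMI below 3 | yes | yes | procedural failure |
| PCI done, then in-hospital CABG, death, AMI, stroke or repeat revascularisation | yes | yes | MACCE |
| PCI attempted only, no vessel treated | no | yes | procedural failure; MACCE only if a component event occurs |
| CABG in the same hospitalisation, no PCI | no | yes | procedural failure and MACCE |

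The last two rows are missing from both tests. The first two are not.

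**2. What else the plan reports on the omitted cases.** Procedural success is summarised by arm in SAF (SAP 8.10, Tables 17/19). MACCE and its components are summarised in SAF (SAP 8.12.1, Tables 50/51). Both summaries are untested and as treated, so an attempt abandoned before the roadmap was used could be grouped under control. Tables 5 and 6 give disposition and reasons for non-completion by randomised arm, but not these two outcomes.

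**3. Inputs for a size.** The documents give no rate of failed attempts or conversions, and no sample size or power for either outcome. The only figure available is the denominator: 177/(1 − 0.1) = 196.7, so 197 per arm and 394 in total, as the plan states. The counts below are assumptions. They take 197 per arm as all attempted procedures and put 2 failures per arm inside the FAP.

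**4. Formula.** With n = 197 in both arms and a and b failures, let m = (a + b)/2 and d = (a − b)/2. The chi-square without continuity correction is 2d²/m + 2d²/(197 − m). In the FAP the expected failure counts are about 2, so half the cells are below 5 and the SAP's rule selects Fisher's test.

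**5. Results (DCR v control).**

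| Omitted | FAP test | All 197 per arm |
|---|---|---|
| 4 v 4 | 2/193 v 2/193, p = 1.00 | 6 v 6 (3.0% each), p = 1.00 |
| 6 v 2 | 2/191 v 2/195, p = 1.00 | 8 v 4 (4.1% v 2.0%), p = 0.24 |
| 8 v 2 | 2/189 v 2/195, p = 1.00 | 10 v 4 (5.1% v 2.0%), p = 0.10 |
| 10 v 2 | 2/187 v 2/195, p = 1.00 | 12 v 4 (6.1% v 2.0%), p = 0.041 |
| 12 v 2 | 2/185 v 2/195, p = 1.00 | 14 v 4 (7.1% v 2.0%), p = 0.016 |

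For the last row m = 9 and d = 5, so chi-square = 50/9 + 50/188 = 5.556 + 0.266 = 5.82 and p = 0.016 (Fisher 0.027). The simple 95% interval, difference ± 1.96·√(p₁(1 − p₁)/n₁ + p₂(1 − p₂)/n₂), is 5.1 points (1.0 to 9.2) over all attempts and 0.1 points (−2.0 to 2.1) in the FAP.

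In the balanced row the difference is untouched. Only the level moves: 2/193 = 1.0% in place of 6/197 = 3.0%. With 4 failures per arm inside the FAP, 12 v 2 omitted gives p = 1.00 in the FAP and 16 v 6, p = 0.028, over all attempts.

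These counts describe procedural success. For MACCE only the omitted subjects with in-hospital CABG or another component event would move, so the effect there is no larger and probably smaller.

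**The case against.** The strongest reply is that little is hidden and little depends on it. The omitted cases are shown by arm in SAF, MACCE with its CABG component and a listing of every case, and non-completion is tabulated by randomised arm. Both outcomes are exploratory, the protocol expects no significant difference in either, and SAP 9.2 declares the change of population. AKI, procedural complications, device deficiencies and time to discharge are also reported, so these two outcomes are not the only clinical checks. The p-values rest on assumed counts. If non-completion is 1 to 3% per arm (2 to 6 of 197), even 6 v 2 with no other failures gives expected counts of 4, hence Fisher's test and p = 0.28.

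Most of this stands, and it limits the weight of the point. It does not supply the missing item, a comparison of these outcomes as randomised over all attempted procedures. An expectation of no difference is also no reason to choose an analysis set that can conceal one.

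A reader might go further and infer that the FAP requires a completed PCI and so removes the failures and events as a class. The documents do not support that. The criterion is a PCI in at least one vessel, so a subject treated in one vessel with failure in another stays in, as do poor results and events after a PCI. The SAP also does not say where a PCI that was begun without success falls between having undergone a PCI and having had an attempt.

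**Conclusion.** The point holds as a limited one. Both between-arm tests omit attempt-only subjects and those sent to CABG without PCI. This exclusion is post-randomisation and outcome-related, and it departs from the protocol's inclusion of all subjects. The cases remain visible in SAF, untested and as treated.

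The size cannot be derived from the documents. Balanced omissions leave the difference unbiased and understate the failure rate. A strong imbalance could turn p = 0.016 into p = 1.00, but only under the assumed 12 v 2, and smaller imbalances such as 6 v 2 would not be significant either way. The conclusion also assumes that an attempt in which no vessel is treated is classed as an attempt and not as a PCI undergone. It bears on how two exploratory outcomes are read, not on contrast volume.

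**What to change.** In SAP 8.11.3.8 and 8.11.3.9:

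- Run both comparisons on all randomised subjects in whom PCI or another procedure was attempted, grouped as randomised, and give the difference with its confidence interval beside the p-value.
- Count attempt-only subjects, and those converted without PCI, as no procedural success. Count in-hospital CABG as MACCE, as the SAP's own definition already does.
- Keep the FAP and PP versions as supportive.

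In SAP 8.2.1, state what separates having undergone a PCI from an attempt. In SAP 9.2, list the MACCE test as an addition to the protocol.

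This set also takes in the OCT and atherectomy subjects, who are replaced but remain in SAF, so its total may exceed 394.

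The cost is SAP wording and two re-run tables, with slightly lower reported success rates. No new data are needed: procedure and discharge data are already listed for SAF, and MACCE for all enrolled subjects.
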